4.2 ELIGIBILITY CRITERIA

4.2.1 INCLUSION CRITERIA

1. Healthy, male and female participant aged 18 to 40 years and available for 26 months
2. Must be at low risk for HIV infection per investigator assessment and using the study risk assessment tool.
3. Must be able to understand and complete the informed consent process.
4. Must be capable of reading English or Kiswahili.
5. Must agree to a home visit.
6. Willing to have photo or fingerprint taken for identification purposes.
7. Must complete a Test of Understanding (TOU) before enrollment. Must answer 9 out of 10 questions correctly, with a maximum of three attempts.
8. Must be in good general health without a clinically significant medical history.
9. HIV-uninfected per diagnostic algorithm within 45 days of enrollment.
10. Laboratory values:
 - **Hemoglobin:**
12.5-18.1 g/dL men
11.0-16.1 g/dL women
 - **White Cell Count:**
2.7-7.7 $\times 10^3$ cells/ μ L men
3.0-9.1 $\times 10^3$ cells/ μ L women
 - **Platelets:**
125-370 10^3 cells/ μ L men
125-444 10^3 cells/ μ L women
- **ALT and AST:** ≤ 1.25 institutional upper limit of the reference range
Creatinine: ≤ 1.25 institutional upper limit of the reference range
- **Urinalysis:** (dipstick) for blood and protein less than 1+ and negative glucose

Female-Specific Criteria:

11. Negative urine pregnancy test for women at screening, the day of each vaccination, and before any invasive procedure.
12. Already using and commits to continued use of an adequate birth control method for 45 days before to the first vaccine/placebo vaccination and for at least 90 days after the final vaccine/placebo vaccination. Adequate birth control is defined as follows: Contraceptive medications delivered orally, intramuscularly, vaginally, or implanted, underneath the skin, surgical methods (hysterectomy or bilateral tubal ligation), condoms with spermicide, diaphragms, intrauterine device (IUD), vasectomy in a monogamous partner, or abstinence.

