4.4.2.3 Early Discontinuation of Vaccinations or Withdrawal of a Study Participant

A participant may have vaccinations discontinued or will be taken out of the study entirely under the following circumstances:

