4.4.2.3.1 Immediate Early Discontinuation

1. Upon learning of pregnancy
2. Due to an SAE that is believed to be related to study vaccination, including
 - a. Any Grade 3 systemic adverse reaction that is assessed as related to the study agent,
 - b. Any Grade 4 adverse event assessed as related to the study agent, and
3. Infection with HIV-1.

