4.4.5 MANAGEMENT OF PARTICIPANTS WHO BECOME INCARCERATED

Participation of prisoners is not planned, and any participant will be suspended from study visits while incarcerated, except visits or telephone contact for ensuring their safety. No study product will be administered to a participant who is incarcerated. The IRB will be notified of the period of incarceration. Data and samples that were collected before the period of incarceration may still be stored and used for analyses. After release from incarceration, either the participant may return to participation in study visits according to the SOE or study participation may be terminated at the discretion of the PI.

Any participant who is incarcerated will be re-consented before rejoining the study.

4.4.6 MANAGEMENT OF PARTICIPANTS WITH VACCINE-INDUCED SEROPOSITIVITY (VISP) OR SEROREACTIVITY (VISR)

Participants who receive study vaccine (not placebo) may subsequently receive a false positive on an HIV antibody test. Participants are asked to contact the PI or study staff if at any time during or after study participation if an HIV test is requested outside of the study. If a participant has an issue due to a false-positive HIV test result from receiving the vaccination, the PI will provide an explanatory letter, and the study will provide re-testing.

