Screening Visit 
 • Study briefing and collection of contact information • Informed consents • Test of understanding • Review medical history including medications • Vital signs (blood pressure, pulse, respiratory rate, and oral temperature) • Complete physical exam including height and weight • CBC, creatinine, ALT, and AST • HIV risk counseling • HIV test with counseling before and after • Hepatitis B and C • Syphilis test • Pregnancy counseling • Urine pregnancy test for women • Urinalysis (dipstick) for blood, protein, and glucose
Optional 
 • Pap smear for women who agree to cervicovaginal secretion collection
Vaccination Visits 
 • Targeted physical exam and review of current medication • Vital signs (blood pressure, pulse, respiratory rate, and oral temperature) • Review eligibility • HIV risk counseling • Blood draw for safety*, research and HIV tests • Pregnancy counseling • Urine pregnancy test for women • Enrollment and randomize* • Administer vaccination or placebo • Post-injection observation for 30-60 minutes • Adverse event documentation • Provide a diary card and instruction
Optional 
 • Mucosal secretion collection*

Phone/Clinic Follow Up Visits after Each Vaccination and as Needed

- Assessment of wellbeing
- Measure vital signs (blood pressure, pulse, respiratory rate, and oral temperature) *if the participant comes to the clinic*
- Review of symptoms
- Adverse event documentation

Telephone follow-up will be the default method for this visit. Home visits will be done for those participants who will not be reachable by phone.

Follow Up Visits to Include Final Visit

- Targeted physical exam and review of concomitant medication
- Measure vital signs (blood pressure, pulse, respiratory rate, and oral temperature)
- Body weight, if clinically indicated
- HIV risk counseling
- Pregnancy counseling
- Urine pregnancy test for women if mucosal secretion collection or lymph node biopsy*
- Review of diary card*
- Adverse event documentation
- Blood draw for safety, research, and HIV tests*

Optional

- Mucosal secretion collection*
- Lymph node biopsy and biopsy site assessment*

* See Appendix A: Schedule of Evaluations

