7: Pregnancy testing must be performed prior to vaccination and mucosal secretion collection

8: 9ml should be taken if CBC/Chem results not available on day of biopsy. Otherwise, 3ml should be drawn

9: Medically Attended Adverse Events will be followed through the end of the study, a full 12 months following the last vaccination

10: Participants will take home the diary card and complete and the diary card will be reviewed at 7 days after vaccination.

11: Additional testing as clinically indicated

12: A participant is considered enrolled into the study once they are randomized into a study group

13: Study vaccination outside of a participant's vaccination window may occur at the discretion of the PSRT.

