APPENDIX G. PARTICIPANT VISIT SCHEDULE

RV460/WRAIR #2672**Appendix G**
Participant Visit Schedule

Visit No.	Visit Day	Clinic visit activities	Optional Procedures	Approx. Time	Reimbursement
Screening	-45 to -3 days	Screening: Briefing & contact information, informed consents, test of understanding, medical history, vital signs, complete physical exam, 1 TBSP blood draw for: HIV test, hepatitis B and C, syphilis, general health, urine pregnancy test for women, urine test (dipstick) for blood and protein	-Pap smear for women who agree to vaginal secretion collection	4-5 Hours	1000 Ksh
1	0	Vaccination 1*: Enrollment & randomize, exam & eligibility review, vaccination or placebo, examine injection site 30-60 minutes post-injection, receive diary card, urine pregnancy test for women, 12 TBSP blood draw for: research tests & HIV	-Mucosal secretion collection	5 - 6 Hours	1000 Ksh (+1000 Ksh for each mucosal secretion collection)
Phone call or Clinic Visit 24-48 hours After Vaccination					1000 Ksh
2	3	Follow Up: exam & symptom review, review diary card, 2 TBSP blood draw for: research tests. Bring diary card.		2 Hours	1000 Ksh
3	7	Follow Up: exam & symptom review, review & collect diary card, 2 TBSP blood draw for: research tests. Bring diary card.		3 Hours	1000 Ksh
4	14	Follow Up: exam & symptom review, 5 TBSP blood draw for: general health & research tests		2 Hours	1000 Ksh
5	28	Vaccination 2*: Exam & eligibility review, vaccination or placebo, examine injection site 30-60 minutes post-injection, receive diary card, urine pregnancy test for women, 2 TBSP blood draw for: research tests		4 Hours	1000 Ksh
Phone call or Clinic Visit 24-48 hours After Vaccination					1000 Ksh

Visit No.	Visit Day	Clinic visit activities	Optional Procedures	Approx. Time	Reimbursement
6	35	Follow Up: exam & symptom review, Review diary card, 2 TBSP blood draw for: research tests. Bring diary card.		2 Hours	1000 Ksh
7	42	Follow Up: exam & symptom review, 4 TBSP blood draw for: research tests and general health. Urine pregnancy test for women that elect for optional procedure(s). Bring diary card.	-Mucosal Secretion collection	4 - 5 hours	1000 Ksh (+1000 Ksh for each mucosal secretion collection)
8	84	Vaccination 3*: Exam & eligibility review, vaccination or placebo, examine injection site 30-60 minutes post-injection, receive diary card, urine pregnancy test for women, 3 TBSP blood draw for: research tests		4 Hours	1000 Ksh

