19	392	Vaccination 6*: Exam & eligibility review, vaccination or placebo, examine injection site 30-60 minutes post-injection, receive diary card, urine pregnancy test for women, 3 TBSP blood draw for: research tests		4 Hours	1000 Ksh
Phone call or Clinic Visit 24-48 hours After Vaccination					1000 Ksh
20	395	Follow Up: exam & symptom review, review diary card, 2 TBSP blood draw for: research tests. Bring diary card.		2 Hours	1000 Ksh
21	399	Follow Up: exam & symptom review, review & collect diary card, 5 TBSP blood draw for: research tests & HIV. Bring diary card.		3 Hours	1000 Ksh

Visit No.	Visit Day	Clinic visit activities	Optional Procedures	Approx. Time	Reimbursement
22	406	Follow Up: exam & symptom review, 11 TBSP blood draw for: general health & HIV & research tests. Urine pregnancy test for women that elect for optional procedure(s).	-Mucosal secretion collection -Lymph node biopsy	5 - 6 Hours	1000 Ksh (+1000 Ksh for each mucosal secretion collection & 5000 Ksh for lymph node biopsy)
Return in 1 week if lymph node biopsy was performed					
23	476	Follow Up: exam & symptom review, 9 TBSP blood draw for: research tests. Urine pregnancy test for women that elect for optional procedure(s).	-Mucosal secretion collection	4 - 5 Hours	1000 Ksh (+1000 Ksh for each mucosal secretion collection)
24	560	Follow Up: exam & symptom review, 9 TBSP blood draw for: research tests & HIV. Urine pregnancy test for women that elect for optional procedure(s).	-Mucosal secretion collection	4 - 5 Hours	1000 Ksh (+1000 Ksh for each mucosal secretion collection)
25	728	Follow Up: exam & symptom review, 9 TBSP blood draw for: research tests & HIV. Urine pregnancy test for women that elect for optional procedure(s).	-Mucosal secretion collection	4 - 5 Hours	1000 Ksh (+1000 Ksh for each mucosal secretion collection)
26 Exit	735	Final visit: exam & symptom review, 4 TBSP blood draw for: research tests		2 Hours	1000Ksh

Reimbursement

Study visits: 1000 Ksh

Unscheduled visits: Up to 500 Ksh, at the discretion of the study doctor

Mucosal collection: 1000 Ksh per each collection

Lymph node biopsy: 5000 Ksh

Transportation: Up to 3000 Ksh, at the discretion of the study doctor

* A study vaccination may be given outside your vaccination window if the protocol safety review team (PSRT) permits.

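### On the Appendix G schedule no HIV test falls in the 154 days before dose 6, and Table 4 leaves unclear whether doses 2 to 6 carry one

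*Protocol*

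**What the plan says.** Three places in the protocol describe HIV testing around the doses.

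- **Section 5.5, Table 4**, vaccination visits: "Blood draw for safety*, research and HIV tests". The asterisk, which points to Appendix A, is on safety and not on HIV. Enrolment with randomisation and mucosal collection, also limited to certain visits, carry one too. In the follow-up list the asterisk comes after HIV tests.
- **Appendix G**, vaccination 1: "12 TBSP blood draw for: research tests & HIV". For vaccinations 2 to 6 (visits 5, 8, 12, 16 and 19) it names research tests only; visit 19 reads "receive diary card, urine pregnancy test for women, 3 TBSP blood draw for: research tests".
- **Appendix A** has an HIV-testing row, but its columns were lost when the PDF was read. That is not a fault of the plan. It does mean that the governing schedule cannot be checked directly here.

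Section 4.4.2.3 introduces the stopping grounds with "A participant may have vaccinations discontinued or will be taken out of the study entirely under the following circumstances", and section 4.4.2.3.1 lists "Infection with HIV-1" among those for immediate early discontinuation. Pregnancy is on the same list. At entry, section 4.2.1 item 9 requires "HIV-uninfected per diagnostic algorithm within 45 days of enrollment". Appendix A footnote 11, attached to the counselling row, allows "Additional testing as clinically indicated".

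**The concern.** A stopping ground works only if someone looks for the condition before the next dose. Pregnancy is looked for: section 4.2.1 item 11 and Appendix A footnote 7 call for a test before every vaccination. On the Appendix G schedule HIV is not, and the longest blind interval comes before the last dose. A participant infected in that interval could receive dose 6 and be referred to care later than necessary. Section 9.2.1.4 says it is unknown whether the vaccines affect the course of disease in someone who becomes infected. Separately, site staff working from Table 4 and from Appendix G could reach different conclusions on whether an HIV sample is due at doses 2 to 6.

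**Working it through.** **1. The plan's own volumes.** The Appendix A cumulative volumes reproduce from the daily volumes. Around dose 6: 1132 + 46 = 1178; + 34 = 1212; + 66 = 1278; + 168.5 = 1446.5 mL. The 8-week totals at visits 19 to 22 also reproduce: 46, 80, 146 and 314.5 mL.

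**2. Gaps before each dose.** Appendix G names HIV tests at screening and on days 0, 98, 154, 238, 399, 406, 560 and 728. Appendix A allows ±7 days for doses 2 to 6 and ±3 days for visits 11, 15 and 18. Gap = dose day − last test day; the range adds or subtracts both windows.

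| Dose | Day | Last test day | Gap (days) | Within windows |
|---|---|---|---|---|
| 2 | 28 | 0 | 28 | 21–35 |
| 3 | 84 | 0 | 84 | 77–91 |
| 4 | 140 | 98 | 42 | 32–52 |
| 5 | 224 | 154 | 70 | 60–80 |
| 6 | 392 | 238 | 154 | 144–164 |

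For dose 6: (392 − 7) − (238 + 3) = 144 and (392 + 7) − (238 − 3) = 164. Dosing outside the window, which the PSRT may permit, could lengthen this.

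**3. Do the Appendix A volumes agree with Appendix G?** Assume that cellular, gene-expression and storage blood comes in 8.5 mL units. Subtracting whole units from the daily volume leaves:

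| Left over (mL) | Visits | Appendix G names |
|---|---|---|
| 24 | 11, 15, 18, 22 | general health and HIV |
| 18 | 1, 24, 25 | HIV, no general health |
| 18 | 4, 7 | general health, no HIV |
| 12 | 5, 8, 12, 16, 19 (doses 2–6); 23, 26 | research only |
| 15 | 10 and 21 | research only at 10; HIV at 21 |
| 6 | 3, 6, 14, 17 | research only |

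Examples: visit 1, 171 − 153 = 18; visit 18, 126 − 102 = 24; visit 19, 46 − 34 = 12.

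Most rows fit 12 mL for the two antibody assays, plus 6 mL for safety and 6 mL for HIV where each applies. On that pattern doses 2 to 6 have no HIV tube. It is not proof: visits 3, 6, 14 and 17 leave only 6 mL, so 12 mL could also be 6 mL antibody plus 6 mL HIV.

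**4. The first test after dose 6.** Appendix G puts it at visit 21 (day 399), 7 days after the dose. But visit 21 leaves 66 − 51 = 15 mL, the same as visit 10 (49 − 34 = 15), where no HIV test is named. Both visits come a week before a biopsy visit, and 15 = 12 + 3 fits the 3 mL pre-biopsy draw of footnote 8. There may be no HIV tube on day 399. If so, the first test is day 406, 14 days after the dose.

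**5. Room for one more tube.** Adding 6 mL at visit 19 gives 8-week totals at visits 19 to 22 of 52, 86, 152 and 320.5 mL. The section 5.5 limit is 450 mL, so 450 − 320.5 = 129.5 mL remain.

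**The case against.** The strongest reply is that Appendix A governs and cannot be read, so Appendix G, a participant handout, is standing in for it. Appendix G may itself be wrong at visit 21. That stands: the 154-day gap is conditional on Appendix G, with the volumes as support only.

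A second reply is that the two complaints undercut each other. If Table 4 applies to every dose, a sample is already scheduled at visit 19; if it is a generic list, nothing is contradicted. In part this stands, since Table 4 is a generic list and is true of dose 1. But the missing asterisk leaves the matter open, and Table 4 does not say that a result must be in hand before the injection.

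Third, the protocol has other protection: low-risk entry criteria, eligibility review and risk counselling at each dose, and testing when indicated. These reduce the risk. They depend on symptoms or a reported exposure, so they do not replace a test.

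Two stronger readings are tempting. A reader might infer that the protocol breaks its own 45-day rule at doses 3, 5 and 6. It does not: that limit applies at enrolment only, and no section requires an HIV test before later doses. A reader might also infer that two HIV tests sit seven days apart just after dose 6, so that one can be moved at no cost. That depends on the day 399 test, which the visit 21 volume puts in doubt.

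**Conclusion.** The point holds as a minor to moderate safety improvement. Table 4 is unclear on HIV testing at doses 2 to 6. On the Appendix G dates, dose 6 follows the last scheduled HIV test by 154 days (144 to 164 within windows), and no scheduled test would find an infection acquired in that interval before dosing. This rests on Appendix G being the schedule actually followed; a legible Appendix A row could confirm or overturn it. The protocol gives no HIV incidence, so the number affected is not estimated; among 126 low-risk adults it is likely small.

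**What to change.** 1. Make Table 4, Appendix A and Appendix G name the same HIV-test visits, and settle whether day 399 has one.
2. Schedule an HIV test at visit 19, or within about 7 days before it, with the result known before dose 6. If the day 399 test exists, move it; the 8-week totals at visits 21 and 22 then stay at 146 and 314.5 mL. If it does not, add one 6 mL tube.
3. Protect the blind. Section 4.4.6 notes that "Participants who receive study vaccine (not placebo) may subsequently receive a false positive on an HIV antibody test", so a reactive or delayed result could hint at allocation. Resolve reactive immunoassays by nucleic acid testing in the laboratory (section 6.1.1.1 already provides for it), report to the site only infected or not infected, and use the same turnaround for everyone.

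Testing before doses 3 and 5 is optional. A further 6 mL at visit 8 would bring the highest affected 8-week total to 315.5 + 6 = 321.5 mL; at visit 16, to 195 + 6 = 201 mL. No blood should be added at visit 5, where 444.5 + 6 = 450.5 mL would pass the limit.

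The cost is a schedule amendment, at most one extra tube for dose 6, possibly a short extra visit, and an occasional dose delay while a reactive result is resolved. Such delays would fall mainly on vaccine recipients, which is why step 3 is needed.

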APPENDIX H. RISK ASSESSMENT TOOL

WRAIR #2672/RV460 HIV Risk Assessment Tool

PID: _____

Date: ____ / ____ / ____

Visit: _____

SEXUAL BEHAVIOURS

A participant may be appropriate for inclusion if he or she meets these guidelines:

Criteria	A participant in the last 12 months:	Yes	No
1.	Did not have oral, vaginal, or anal intercourse with an HIV-infected partner, or a partner who uses injection drugs.		
2.	Did not give or receive money, drugs, gifts, or services in exchange for oral, vaginal, or anal sex		
3.	Has not been diagnosed and/or been treated for a sexually transmitted infection: OR have not had any of the sexually transmitted infection symptoms as assessed by the study doctor/clinician.		
Criteria	In the last 6 months:		
1.	Has abstained from penile/anal or penile/vaginal intercourse. OR had 2 or fewer partners of the opposite birth sex for vaginal and/or anal intercourse.		
2.	Is not an MSM or a transgender person.		
3.	Uses or intends to use condoms in situations which may include penile/anal or penile/vaginal intercourse with new partners, partners of unknown HIV status, occasional partners, partners outside a primary relationship, and/or partners known to have other partners.		

NON-SEXUAL BEHAVIOURS

Criteria	A participant who in the last 12 months:		
1.	Did not inject drugs or other substances without a prescription.		
2.	Did not use cocaine, methamphetamine, or excessive alcohol, which in the investigator's judgment, rendered the participant at greater than low risk for acquiring HIV infection		

Comments:

Signature of Investigator or Designee

Date

APPENDIX I. DIARY CARD

LABEL

Diary Card

Participant ID: | 4 | 6 | 0 | - | | | | | |

Vacc. #: _____

Vaccination Date: _____

DD

MM

YYYY

Short title: Comparative Adjuvant Study for HIV-1 Env DNA and Protein Vaccines in Kenya
 RV460 / WRAIR #2672

13-07-2020
 Version 1.7

Instruction for recording No. 2-7 and 8-15

Please use the grading scale below to record the severity of your reaction to the injections in the next sections:

0 = None**1 = Mild:** minimal interference with usual social and functional activities.**2 = Moderate:** symptoms causing greater than minimal interference with usual social and functional activities.**3 = Severe:** symptoms causing inability to perform usual social and functional activities

Time After vaccination	30-60 min	6 hr	Day 1	Day 2	Day 3	Day 4	Day 5	Day 6	Day 7
Day/Month	__ / __	__ / __	__ / __	__ / __	__ / __	__ / __	__ / __	__ / __	__ / __
Time taken (hrs/min)									
1. Oral temperature (Celsius)									

Vaccination injection site reactions		 Right arm		 Left arm	
2. Injection site pain or tenderness					
3. Swelling (at injection site)					
4. Itching (at injection site)					
5. Redness (measure the largest dimension in cm.)					
6. Hardness (measure the largest dimension in cm.)					
7. Warmth (at injection site)					

General Reactions (not injection site)								
8. Headache								
9. Chills								
10. Dizziness								
11. Tiredness / Fatigue								
12. Nausea								
13. Muscle pain								
14. Joint pain								
15. Rash (if present, describe in "other symptoms")								
16. Took medication for fever or for above symptoms?	0=No 1=Yes							

Other symptoms (please describe):								

LABEL

Diary Card

Participant ID: | 4 | 6 | 0 | - | | | | |

Vacc. #: _____

Vaccination Date: _____

DD

MM

YYYY

Short title: Comparative Adjuvant Study for HIV-1 Env DNA and Protein Vaccines in Kenya
 RV460 / WRAIR #2672

13-07-2020
 Version 1.7

If you take any medication, please record in the table below
 If you take medications for fevers, please check your temperature again after 4 hours and record above in "Other symptoms"

Medication	Dose/route	Reason	Start date	Stop date

Suggestion

- Complete the diary card in as much detail as you can every day, at the same time each day
- Record any problems that occur during this period
- Bring back this diary card with you at the next appointment
- If you forget to record any data, leave it blank

If you have any problems or questions, please contact:

Staff name _____ Telephone Number _____

If you received a "patch" over the vaccination site on your upper arm, please write the time you removed the "patch" in the space below. You will need to wear the patch for 6 hours \pm 2 hours (range 4-8 hours) after application.

Time patch was removed: _____ (hrs/min)

Official use only

Card completed by participant and not edited by staff

Card completed by participant and edited by:

Staff name _____

DD

MM

YYYY

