8 SAFETY AND REPORTING

8.1 ASSESSING AND RECORDING SAFETY PARAMETERS

8.1.1 REACTOGENICITY

8.1.1.1 Diary Card (7-Day Solicited Reactogenicity)

Reactogenicity events are AEs that are common and known to occur following administration of this type of study vaccine. A diary card will be used to aid in the collection of potential reactions.

Temperature and solicited local and systemic symptoms will be recorded in the clinic before vaccination and 30-60 minutes post-injection, at home about 6 hours after vaccination, and then daily by the participant for 7 days. Solicited symptoms that persist after the end of day 7 will be considered an AE or SAE, will be documented, and followed through resolution.

At each vaccination visit, participants will be given a new diary card, a thermometer and a ruler. The diary card will be used as a memory aid, on which the participant will record oral temperature, local and systemic symptoms, and concomitant medications daily for 7 days, beginning with the day of vaccination. Participants will be trained to complete the diary card, how to use the thermometer, and how to measure injection site swelling and redness using the ruler after each vaccination. Completion of the diary card training will be noted in source documents. The diary card is not a source document; the information gained from the review of the diary card and the interview with participants will be documented using a combination of progress notes and CRFs maintained in the participants research chart.

The solicited signs and symptoms on the diary card are:

Local

- Pain/tenderness
- Itching
- Warmth
- Redness/erythema measurement of largest dimension
- Swelling/induration measurement of largest dimension

Systemic

- Fever
- Myalgia
- Arthralgia
- Headache
- Fatigue
- Chills
- Rash
- Nausea

- Dizziness

Where multiple assessments are taken on the same day, participants will be requested to record the day's highest measured temperature and measurement of largest dimension for redness and swelling.

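### The diary card puts redness and hardness under both a 0-3 activity scale and a size in cm, and gives swelling no size prompt although section 8.1.1.1 treats it as a measured sign

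*Protocol*

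**What the plan says.** Appendix I (Diary Card) heads its scoring instruction "Instruction for recording No. 2-7 and 8-15" and defines the scale as 0 = none, then 1, 2 and 3 by increasing interference with usual activities. It makes no exception within items 2-7.

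Three local rows matter here:

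- Redness: "5. Redness (measure the largest dimension in cm".
- Hardness: "6. Hardness (measure the largest dimension in cm".
- Swelling: "3. Swelling (at injection site", with nothing about size.

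Among its closing suggestions the card adds "If you forget to record any data, leave it blank".

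Section 8.1.1.1 describes the same data differently. Its list of local signs has "Swelling/induration measurement of largest dimension" as one entry. Participants receive a ruler and are trained in "how to measure injection site swelling and redness using the ruler after each vaccination". Where several assessments fall on one day, they are asked for the "measurement of largest dimension for redness and swelling". When the card is reviewed, missing local and systemic information may be supplied from recollection, but swelling, redness and temperature measurements are excepted.

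Solicited local reactogenicity is part of the primary endpoint (sections 1.2.1 and 2.7.1), and section 7.2.2 reports maximum severity per participant.

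**The concern.** A participant who follows the heading writes a grade in the redness and hardness rows. One who follows the row label writes centimetres. The cell has no unit and no second field, so the entry does not show which was done. For swelling the problem is the opposite: the card as printed asks only for an activity grade, so the size that section 8.1.1.1 trains participants to take has no place of its own.

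At stake is the local part of a primary endpoint summarised by the worst value per participant. A single misread peak entry that nobody queries could, in principle, set a participant's reported maximum. With 15 vaccinees per group, one participant is 1/15 = 6.7 percentage points of a group's proportion.

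**Working it through.** No statistical figure in the plan is in question, so the check is a comparison of the two texts and a count of rows.

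**Rows under the 0-3 instruction.** Items 2-7 are 6 local rows and items 8-15 are 8 general rows, 14 in all.

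**Rows with two instructions.** Items 5 and 6 are in the range 2-7 and also ask for cm: 2 of the 6 local rows.

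**Row with no size prompt.** Item 3: 1 of the 6 local rows. Together, 3 of 6 local rows do not fit either the card's own heading or section 8.1.1.1.

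**Which entries are ambiguous.** A 0 means none on either scale. A decimal, or a value above 3, can only be a size. The ambiguity is therefore confined to entries of exactly 1, 2 or 3 in items 5 and 6.

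**Is swelling size captured elsewhere on the card?** In part. Section 8.1.1.1 treats swelling/induration as one sign, while the card splits it into item 3 (swelling) and item 6 (hardness). Item 6 takes a dimension in cm, so the induration half is covered. Swelling that is not hard has no measured row, although the ruler training names swelling itself.

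**Can review repair the entries?** The two defects differ.

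- Items 5 and 6: the entry is present but unclear. The recall exception concerns missing measurements, so nothing stops the clinician from asking whether a 2 was a grade or centimetres. The answer settles the scale used; it does not supply a size that was never taken.
- Item 3: if no size was written, the swelling measurement is missing, and section 8.1.1.1 does not allow it to be filled in by recall.

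**When review happens (Appendix G).**

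- Vaccinations 1, 3, 4 and 6: examination and card review at day 3 (visits 2, 9, 13 and 20), and again at about day 7 (visits 3, 10, 14 and 21).
- Vaccinations 2 and 5: no day-3 visit. The first examination with card review is at about day 7 (visits 6 and 17). Before that there is only the contact 24 to 48 hours after vaccination, by telephone by default (section 5.5, Table 4).

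A mix-up can thus be caught mid-week after four of the six vaccinations. After the other two it can go uncorrected for about a week.

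**The case against.** The strongest reply is that the card is not the data. Sections 8.1.1.1 and 11.1 call it a memory aid and not a source document. What reaches the CRF comes from card review plus interview, the card has a field for staff edits, and section 8.1.7 grades severity with the DAIDS table. The rows for redness and hardness carry their own specific instruction, and participants are trained and given a ruler. The section 8.1.1.1 request for the day's largest dimension of redness and swelling applies only where several assessments are made on one day. The DAIDS size thresholds are not in the protocol, so nobody can show how far a grade would move.

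Most of this stands and limits the consequence. It does not remove the contradiction: the listing of swelling/induration as a measured sign and the ruler training carry no such condition, and the heading still overrides the row labels for anyone who reads it literally.

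A reader might go further in three ways that the documents do not support:

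- That ambiguous redness entries are unrecoverable because of the recall exception. That clause covers missing measurements, not unclear ones, and does not name hardness.
- That the reported grades will be biased. Neither a direction nor a frequency of misreading can be derived. Counts of printed cells or cards would describe the form, not affected data.
- That cards may be taken away before Day 7 is filled in, because review is allowed at day 7 ± 2 and Appendix G has the card collected at some of those visits. No text orders an unfinished card to be taken, footnote 10 of Appendix A puts completion before review, and section 5.3 already requires the sentinel reviews to cover data through Day 7. Moving sentinel visits later in the window would also shift research sampling in Groups 2-7 only.

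**Conclusion.** The point holds as a contradiction within the card (items 5 and 6) and between the card and section 8.1.1.1 (item 3). It touches 3 of 6 local rows, and for redness and hardness only entries of 1, 2 or 3. The likely effect on the primary reactogenicity endpoint is small where review works as described, and larger after vaccinations 2 and 5, where there is no day-3 visit. The firmest loss is swelling size, which the card does not prompt for and which may not be recovered by recall.

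This rests on the card being used as printed in Appendix I (version 1.7). If site training or the CRF already separates grade from size, the practical effect shrinks further, but the card and section 8.1.1.1 would still disagree. The form feeds a primary endpoint and the correction is cheap, so it should be made.

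**What to change.** In Appendix I:

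1. Limit the 0-3 instruction to items 2, 4, 7 and 8-15. Alternatively, keep it for all items but give each measured row two labelled fields, one for grade and one for cm.
2. Give item 3 a prompt for the largest dimension in cm, or merge items 3 and 6 into a single swelling/induration row measured in cm, to match section 8.1.1.1. If rows are merged, renumber the items in the scoring instruction accordingly.

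The cost is one new card version. No visit, sample or analysis changes.
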